7.4. Subject Nourishment

The site should provide meals, snacks and beverages to the subject during the Day 1 (Visit 2) and Day 28 (Visit 6) pharmacokinetic and pharmacodynamic sampling times.

7.5. Duration of the Study

The anticipated time for study enrollment is 3 to 6 months. The duration of the screening period is up to 30 days. The expected double-blind treatment period for each subject is 29 days (maximum of 28 days of study medication application). The post-treatment follow-up period is up to 33 days (30 + 3-day window). The maximum total study duration for the double-blind period from the subject's first visit (Visit 1) through the subject's last visit (Visit 8) is 92 days. On Day 1 (Visit 2) and Day 28 (Visit 6), subjects are required to be confined at the investigational center until all study procedures are completed. The confinement period may last approximately 10 hours. The duration of the total study participation from Baseline (Visit 2) to the open-label post-treatment follow up visit, Week 56 (Visit 16) is anticipated to be a maximum of 400 days. The duration of the open-label extension (OLE) should be based on the date of the visit that the subject initiated OLE treatment rather than the days from Baseline (Visit 2). For subjects who entered the open-label extension and had a gap between Visit 7 and entry into the open-label extension due to an administrative delay total study participation may be longer than 400 days.

8. STUDY TREATMENT

8.1. Investigational Study Medication

The study medications for the double-blind period of this study are ATI-50002 Topical Solution, 0.46% and Vehicle Topical Solution. The study medication for the open-label period is ATI-50002-Topical Solution, 0.46%. The study medications are thin clear solutions that are indistinguishable as packaged and labeled. The inactive ingredients include: water, Transcutol P, propylene glycol, polyethylene glycol 400, dimethyl sulfoxide (DMSO), Kolliphor CS 20, benzyl alcohol, poloxamer 188, and povidone K30.

STUDY MEDICATION INFORMATION			
	Double-Blind Period	Open-Label Period	
Study medication name	ATI-50002	Vehicle	ATI-50002
Dosage Strength	0.46%	-	0.46%
Manufacturer	PMRS, Inc., Horsham, PA		
Pharmaceutical Form	Topical Solution		
Container	Amber Glass Bottle, 120 mL with screw cap		
Storage Conditions	59°F to 77°F (15°C to 25°C)		
Dose regimen			
Route	Topical		
Frequency	Twice-daily (Except for Day 1/Visit 2 and Day 28/Visit 6)		
Duration of administration	28 days	52 weeks	

STUDY MEDICATION INFORMATION		
	Double-Blind Period	Open-Label Period
Other supplies	Disposable, single-use droppers will be provided. Applicators for eyebrow application will be provided (open-label)	

8.2. Subject Randomization

Prior to the start of the study, Aclaris Therapeutics, Inc. or a designated third party will generate a list of randomization numbers that shall be transmitted to the assigned clinical packaging organization for study medication labeling. The randomization list will be stored with access limited to designated personnel for study medication labeling. The randomization list will be made available, as appropriate, to unblind the database.

For the double-blind period, subjects will be assigned to 1 of the 2 treatment groups in a random manner and at a 2:1 ratio. At Baseline (Visit 2), an investigational center staff member will assign study medication to eligible subjects by selecting an appropriate Subject Kit. The staff member must select Subject Kits in chronological sequence and in an ascending numerical order starting with the lowest available Subject Kit number. No Subject Kit number may be omitted or reused. The Subject Kit number is the randomization number.

The investigational staff member randomizing the subject will enter the subject identifier, subject initials, and date randomized on both parts of the Subject Kit label, remove the tear-off part, attach it to the subject's study medication label page and record the Subject Kit number in the subject's eCRF.

The 52-week (12 month) extension is open-label, all eligible subjects will receive ATI-50002 Topical Solution, 0.46%.

8.3. Application of Study Medication

At Visit 2 (Day 1), the investigational center staff member will instruct each subject to apply a minimum of 1.5 mL up to a maximum of 4-mL dose of ATI-50002 Topical Solution, 0.46% or Vehicle Topical Solution, twice-daily to the entire scalp; once in the morning and approximately 12 hours later following the instructions in APPENDIX 1. On Day 1 (Visit 2) and Day 28 (Visit 6), study medication will be applied once-a-day due to the 24-hour PK and PD assessments. The subject must wash his/her hands thoroughly before and after each study medication application. The predose PK sample should be drawn and the baseline PD scalp biopsy should be obtained prior to study medication application. The subject should apply a thin film of the assigned study medication to his/her entire scalp and gently rub in the study medication.

On Day 1/ Baseline (Visit 2) the investigational staff member will:

- Dispense the appropriate study medication bottle.
- Weigh the bottle with the cap prior to the first study medication application and record in the subject's source document.
- Instruct the subject on the appropriate application technique (APPENDIX 1).

- Instruct the subject not to apply study medication to the biopsy site and to avoid contact with the eyes.
- Observe the subject's first study medication application to ensure proper coverage and monitor the subject for at least 20 minutes. Collect the study medication bottle.
- Record the first application completion time.
- Weigh the bottle with the cap after study medication application and record the weight in the subject's source document.
- Redisperse study medication after the 24-hour PK and PD blood and biopsy sample collections on Day 2 (Visit 3).

On Day 28 (Visit 6) the investigational staff member will:

- Collect and weigh all study medication bottles (with the cap on the bottle) returned from the subject and record weight(s) in the subject's source document.
- Select one study medication bottle for the Day 28 (Visit 6) application.
- Weigh the bottle and cap prior to study medication application and record weight in the subject's source document.
- Review the application instructions with the subject (APPENDIX 1).
- Instruct the subject to avoid contact with the eyes.
- Observe the subject's study medication application to ensure proper coverage. Collect the study medication bottle after application.
- Record the study medication application completion time in the subject's source document.
- Weigh the bottle and cap after study medication application.
- Do not return the study medication bottle to the subject.

8.4. Study Medication Weights

On Day 1 (Visit 2) and Day 28 (Visit 6), a study staff member will weigh the study medication bottles with the cap prior to and after study medication applications. At the other study visits (Visit 3-15), the staff will weigh the bottles with the cap prior to dispensing new bottle(s) to the subject and after collection of used bottles from the subject. The weights of the study medication bottles must be recorded in the subject's source documentation. Bottles that are not dispensed to the subject do not need to be weighed.

8.5. Treatment Compliance

The investigator or designee will be responsible for monitoring subject compliance by reviewing the amount of study medication used based on the weight of the used study medication bottles and by querying the subject on usage at each visit. At Visits 4-15, an investigational center staff member must query each subject to determine compliance with the study medication application procedure and frequency. The staff member will document the study medication usage in the source document and eCRF. Study staff will counsel the subjects, as required to make sure subjects are compliant with study medication applications.

8.6. Dose Modification

Subjects should be instructed not to modify the study medication application procedure or frequency. All application modifications must be reported on the appropriate source document

and eCRF. If the subject experiences any significant application site AE(s), after discussion with the Sponsor, the investigator or designee may direct the subject to reduce study medication application frequency to once a day. Every effort should be made to resume twice daily applications for the week prior to Day 28 (Visit 6). If a subject cannot resume twice-daily applications to the scalp for more than 4 consecutive days, the subject must be removed from the study. Refer to Section 10.2.4 for Study Medication Interruption or Discontinuation due to related SAEs or specific abnormal laboratory values.

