
16. Participation in an investigational drug or device trial in which administration of an investigational study drug or device occurred within 30 days or 5 half-lives (whichever is longer) of Screening (Visit 1). Subjects who have participated in a study of an investigational drug, device or biologic agent for alopecia areata (AA, AU or AT) within 1 year of screening will be eligible to participate only with individual permission from the Medical Monitor.
 
17. Sensitivity to any of the ingredients in the study medications.
 
18. History of or current alcohol or drug abuse within 2 years of assessment for study enrollment.
 
19. Screening ECG findings of:
 
 • QTcF >450msec for males or >470msec for females (use of the ECG algorithm is acceptable for this purpose) • Heart rate < 45 or > 100 beats/minutes (inclusive) • Rhythm disturbance other than sinus arrhythmia or ectopic supraventricular rhythm (ectopic atrial rhythm) • Conduction disturbance including PR >240msec, pre-excitation (delta wave and PR <120msec), second degree or higher AV block • Acute or chronic signs of ischemia • Left Bundle Branch Block • Prior myocardial infarction 		

Duration of Treatment
 
Double-blind Treatment
 
Screening period up to 30 days.
 
Double-blind treatment period is 29 days (maximum of 28 days of study medication application).
 
Post-treatment Visit 16 is up to 33 days (30 +3 days) following Day 29 for subjects not continuing into the open-label extension.
 
Total study participation for subjects from Baseline (Visit 2) through Post-treatment Visit 16(Day 59 + 3 days) is up to 62 days (29 + 33).
 
Double-Blind + Open-Label Extension
 
The duration of the total study participation from Baseline (Visit 2) to Week 56 (Visit 16) is anticipated to be a maximum of 400 days (393 + 7 days).
 
The duration of the open-label extension (OLE) should be based on the date of the visit that the subject initiated OLE treatment rather than the days from Baseline (Visit 2). For subjects who entered the open-label extension and had a gap between Visit 7 and entry into the open-label extension due to an administrative delay total study participation may be longer than 400 days.
		

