6.8. Subject Withdrawal Criteria

Subjects will be informed that they are free to withdraw from the study at any time and for any reason. The Investigator may remove a subject from the study if, in the Investigator's opinion, it is not in the best interest of the subject to continue the study. Examples of other reasons subjects may be discontinued from the study are: a change in compliance with an inclusion or exclusion criterion, occurrence of AEs, occurrence of pregnancy or use of a prohibited therapy. The Investigator or designee must inform the Aclaris Therapeutics, Inc. study monitor of any subject discontinuation. (Refer to Section 10.2.4 for study medication discontinuation or termination criteria).

In case of premature discontinuation of study participation, all efforts will be made to perform all Week 56 (Visit 16) assessments. The date the subject is withdrawn from the study and the reason for discontinuation must be recorded in the subject's electronic case report forms (eCRFs). All withdrawn subjects with ongoing AEs will be followed until the event has resolved or stabilized, until the subject is referred to the care of a local health care professional, or until a determination of a cause unrelated to the study medication or study procedures is made.

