10.1.4. Adverse Event Reporting Period

The investigator must start reporting non-serious AEs with the subject's first study medication application and continue reporting until the end of the subject's last study visit. Reporting for SAEs must start when the subject signs the ICF and continue until the end of the subject's last visit.

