10.2. Reporting Procedures

10.2.1. Procedures for Reporting Adverse Events

At each post-enrollment visit, the investigator will question the subject to elicit AEs using a non-directive question such as “Has there been any change in your health since the previous study visit?” If appropriate, based on the subject's response to non-directed questioning to elicit AEs, the investigator will follow-up with directed questions and appropriate evaluations.

Any AE noted during the reporting period must be reported in the source documents and on the appropriate AE eCRF. AEs that are defined as “Not Related” to the study medications will be followed until they are resolved or until the subject’s last study visit. AEs that are defined as “Related” to the study medications will be followed until they are resolved or, if not resolved after the subject’s last study visit, until in the opinion of the investigator, the AE reaches a clinically stable outcome with or without sequelae.

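### Section 8.6 takes a subject who cannot sustain twice-daily dosing out of the study, not only off drug, so scheduled double-blind safety checks are lost in the least tolerant subjects

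*Protocol*

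**What the plan says.** Protocol 8.6 lets the investigator, after discussion with the sponsor, cut application to once a day for a significant application-site adverse event. It asks that twice-daily use be restored for the week before Day 28, and then sets the limit: "If a subject cannot resume twice-daily applications to the scalp for more than 4 consecutive days, the subject must be removed from the study". Section 10.2.4.2, which covers severe infection, anaphylaxis and marked laboratory toxicity, only discontinues study medication permanently. It does not itself end participation.

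For anyone who leaves early, 6.8 says: "In case of premature discontinuation of study participation, all efforts will be made to perform all Week 56 (Visit 16) assessments". No day or window is attached. The same section protects events already under way: "All withdrawn subjects with ongoing AEs will be followed until the event has resolved or stabilized".

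New events are found at visits. Section 10.2.1 says: "At each post-enrollment visit, the investigator will question the subject to elicit AEs". Under 10.1.4, reporting of non-serious events stops at the last study visit, and the serious-event rule has the same end: "Reporting for SAEs must start when the subject signs the ICF and continue until the end of the" subject's last visit. SAP 4.4.1 counts an event as treatment-emergent up to 30 days after the last application.

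For subjects who do not enter the extension, the Synopsis places the last visit relative to Day 29: "Post-treatment Visit 16 is up to 33 days (30 +3 days) following Day 29 for subjects not continuing into the open-label extension". The schedule in 7.3 gives it as Day 59 ± 3.

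**The concern.** Safety and tolerability are part of the primary objective, and this rule acts on the subjects with persistent local intolerance. A drug-only stop is already used in 10.2.4.2 for more serious toxicity, so a local reaction that prevents twice-daily use carries the heavier consequence for follow-up.

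After baseline, the double-blind period has only two ECG and laboratory time points, Days 15 and 29. A subject removed before Day 15 has neither, and everything then rests on one exit visit that 6.8 does not date. An early exit visit closes event reporting before the treatment-emergent window has run. A late one means that the only post-baseline ECG and laboratory results come long after exposure ended. SAP 4.4.4 would still count that late ECG in the double-blind shift summary, because follow-up ECGs of subjects who did not enter the extension are assigned there.

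**Working it through.** The plan gives no figure for this loss, so the check is a direct count.

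**Inputs**
- Remaining double-blind visits after Day 2: Visit 4 on Day 8, Visit 5 on Day 15, Visit 6 on Day 28, Visit 7 on Day 29 (Protocol 7.3).
- Post-baseline ECG and laboratory tests: Days 15 and 29 (7.3; 9.5.5 for ECG). Physical exam: Day 29 (9.5.2).
- Twice-daily use is possible on Days 2 to 27, because Days 1 and 28 are once daily (4.1, 7.1).
- Visit 16 without the extension: Day 59 ± 3 (7.3).
- Treatment-emergent window: 30 days after the last application (SAP 4.4.1).

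**Assumptions.** Removal is on the 5th consecutive reduced day, which is also the day of the last application. Visits are on their nominal days, and a visit on the removal day is attended.

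**Step 1: visits lost.** Removal day = first reduced day + 4. The earliest is 2 + 4 = 6 and the latest is 23 + 4 = 27, giving 27 − 6 + 1 = 22 possible days.

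| Removal day | Possible days | Visits remaining | ECG and laboratory points lost |
|---|---|---|---|
| 6–7 | 2 | 4 (Visits 4–7) | Days 15 and 29 |
| 8–14 | 7 | 3 (Visits 5–7) | Days 15 and 29 |
| 15–27 | 13 | 2 (Visits 6–7) | Day 29 |

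Check: 2 + 7 + 13 = 22. These are counts of days, not probabilities. Visits 6 and 7 are on consecutive days and no ECG or laboratory test is scheduled at Visit 6, so the last row is in effect one safety time point.

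Moving removal one day later (up to Day 27), or placing visits at the late edge of their windows, leaves the range at 2 to 4. At the early edge it is 2 to 3.

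**Step 2: exit visit at Day 59 ± 3 (Days 56 to 62).** Unreported days = max(0, 30 − days from last application to exit visit).
- Shortest gap: 56 − 27 = 29 days, so 30 − 29 = 1 day unreported. Every other combination gives 1 or 0.
- For removal on Days 6 to 14, this visit supplies the first post-baseline ECG and laboratory tests. At nominal Day 59 that is 59 − 14 = 45 to 59 − 6 = 53 days after stopping. With the window it is 56 − 14 = 42 to 62 − 6 = 56 days.

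**Step 3: exit visit held early.** The documents name no early timing, so these values are illustrative.

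| Exit visit, days after last application | Unreported days of the 30 |
|---|---|
| 0 | 30 |
| 7 | 23 |
| 14 | 16 |
| 27 | 3 |
| 30 or more | 0 |

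**Step 4: if the scheduled visits are kept.** For removal on Days 6 to 14, the first post-baseline ECG and laboratory tests come on Day 15, which is 15 − 14 = 1 to 15 − 6 = 9 days after stopping. For removal on Days 15 to 27, the Day 29 set comes 29 − 27 = 2 to 29 − 15 = 14 days after stopping.

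**The case against.** **Visit 16 is not undated everywhere.** The schedule gives an absolute Day 59 ± 3, and 7.5 gives a post-treatment follow-up of up to 33 days. Section 7.1 applies Visit 16 to subjects not eligible for the extension, and 8.9.1 makes completion of double-blind treatment a condition of eligibility, so a removed subject can be read as not eligible. This stands. A reader might infer that most of the 30-day window is lost by design. The documents do not support that: under the Day 59 reading the loss is 0 to 1 day, and larger losses arise only if the site holds the exit visit early. What remains is that 6.8 does not say which applies, and that the Day 59 reading delays the ECG and laboratory tests.

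**The SAP window classifies events and does not promise observation.** A subject who completes double-blind treatment and is seen on Day 56 has 56 − 28 = 28 days of observation after the last application. This stands, and is a reason not to treat a loss of a day or two as a defect.

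**The main tolerability signal is kept.** A reader might infer that data on the intolerant subjects disappear. They do not. The triggering event is recorded, ongoing events are followed under 6.8, related events are followed past the last visit under 10.2.1, and the Visit 16 ECG, laboratory tests, vital signs and physical exam are sought.

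**The rule might be thought to apply only in the last week.** The preceding sentence of 8.6 concerns the week before Day 28, but the removal sentence has no time limit. Its plain reading is any time, so this is not a material ambiguity.

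**Ending dosing is a defensible choice in a 28-day twice-daily PK and PD study.** That justifies stopping drug and omitting PK samples. It does not require ending safety follow-up.

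**The visits would yield off-drug data.** This is true, but results 1 to 14 days after stopping are more useful for safety than results about 7 weeks after.

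**Conclusion.** The point holds in a limited form. Applied as written, 8.6 replaces 2 to 4 scheduled double-blind visits with one best-effort exit visit. It costs both post-baseline ECG and laboratory time points for removal on Days 6 to 14, and one for removal on Days 15 to 27. The exit visit then has either a small reporting gap with late ECG and laboratory tests, or prompt assessments with a longer reporting gap, depending on how the site fills the silence in 6.8.

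That visits are dropped is inferred from removal from the study together with the substitution in 6.8; no sentence says so outright. The counts rest on removal on the 5th reduced day and nominal visit days. The documents give no expected removal rate, so the frequency is unknown. Subjects are not replaced (6.7), so one removal affects 1 of 8 active subjects (12.5%) or 1 of 4 vehicle subjects (25%).

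This does not undermine the trial's conclusions: it has no formal power calculation, and SAP 4.8 drops the adverse-event chi-square test. It is an inexpensive improvement that should be made.

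**What to change.** - **Section 8.6.** Replace the removal from the study with an instruction that study medication must be stopped. Keep consenting subjects on the already scheduled double-blind safety visits through Visit 7: adverse events, vital signs, Day 15 and Day 29 laboratory tests and ECG, and the Day 29 physical exam. Omit the Day 29 PK biopsy, the PK blood draws and the in-office application.
- **Section 6.8, subjects who stop in the double-blind period and stay in follow-up.** Place Visit 16 at 30 (+3) days after the later of the last application and Visit 7. With Visit 7 on Day 29 this is Days 59 to 62, within the Synopsis limit of 62 days, and it covers the full 30-day window.
- **Section 6.8, subjects who decline further visits.** Do the Visit 16 assessments promptly at exit, with an adverse-event contact at 30 days if the subject agrees. A blanket rule of no visit before 30 days would delay these subjects' exit ECG and laboratory tests and should be avoided.

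Extension eligibility does not change, because 7.1 already excludes subjects with tolerability issues. The cost is a wording amendment with IRB/EC approval, 2 to 4 already scheduled visits for a subject off drug, and some data that must be flagged as off drug. No extra biopsy or procedure is needed.

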8.7. Study Medication Accountability

The Investigator or designee is responsible for ensuring accountability for the investigational study medication, including reconciliation of study medications and maintenance of study medication records. Upon receipt of study medication, the clinical site will check for accurate delivery and acknowledge receipt by signing (or initialing) and dating the documentation provided. One copy of this document will be returned to Aclaris Therapeutics, Inc. (or designee) and one copy will be maintained in the study file. In addition, an accurate study medication disposition record will be kept up to date, specifying the amount dispensed for each subject and the date of dispensing. This inventory record will be available for inspection at any time. The original inventory record will be available for review by Aclaris Therapeutics, Inc. upon request. At the completion of the study, all used and unused study medication bottles will be returned to Aclaris Therapeutics, Inc. (or designee) for disposal per Aclaris Therapeutics, Inc. (or designee) written instructions. Alternatively, drug disposal may be completed by the investigative site (following appropriate monitor review of inventory) if the site has a written procedure in place dealing with destruction/disposal of investigational products.

